4. STUDY DESIGN

1. Design

D.4. Phase 2: Preliminary effectiveness pilot randomized controlled trial.

Overview. QL registration agents, coaches and/or research staff at Optum will screen for CB use and other study eligibility criteria and enroll participants into their respective state quitline. Once confirmed eligible, consented participants will complete the baseline assessment and be randomized into standard QL treatment as usual (TAU) or the experimental treatment, QL-CBCU. Approximately 3 months after randomization, we will email participants a link to the follow-up survey (with instructions). For those who fail to complete the online survey after two emails, we will send participant contact information via a secure transmission protocol to an external survey group who will attempt to complete the survey by phone, making 11 attempts at

different times of day and on different days. Those who do not complete the interview within 14 days will be emailed a reminder to take the full online survey or an optional brief online survey. Our research team will monitor completed surveys to identify those who reported they had not smoked tobacco in the past 7 days and request a biochemical validation test from participants as explained below (See section D.8.2. Biochemical Validation).

D.4.1. Setting. Participants will primarily be recruited from incoming callers from four state tobacco QLs with fully legalized CB use (Alaska, Washington DC, Oregon, Washington). See letters of support. These four QLs offer four or five proactive coaching calls, mailed support materials, access to text messaging, and web-based programs, plus at least two weeks of free NRT. If recruitment rates are slow, an alternative strategy of recruiting from social media (e.g., Reddit) will be implemented. All eligibility criteria will remain the same.

There will be two behavioral interventions tested in this trial; the standard quitline (treatment as usual: TAU) and the standard QL plus an adapted version of the CBCU (QL-CBCU). Both are phone based, brief, and utilize similar behavior change techniques: motivational interviewing (MI) and cognitive behavioral therapy (CBT). Both interventions include 4-5 proactive counseling calls, mailed materials, and at least 2 weeks of NRT. The new QL-CBCU intervention is being designed to be integrated into the quitline setting and delivered by quitline coaches with minimal training and infrastructure adaptation.

1. Duration

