All counseling calls will be attempted at least five times over different days. We will increase retention at the 3 month follow up survey by reminding participants during coaching calls, notifying participants by email that their survey is due, and offering the survey first via email with a link to the online survey. For those who do not complete the online survey, we will have an external survey company attempt to reach participants by phone, making 11 attempts to reach them on different days and at different times. Finally, if participants have not responded to the phone survey, we may email participants a reminder via email containing links to take the full online survey or optional brief survey. We may follow up with participants who only partially

completed the survey online to troubleshoot any issues completing the survey online offer opportunity to complete survey by phone. Participants will receive an invitation for a post intervention interview with the PI or Co-I and receive \$25 upon completion, for a total of up to \$145 in incentives. Strategies such as these have proven to be effective in our quitline research studies resulting in higher recruitment and retention rates.

4. Data Collection

The sources of research materials obtained from individual human subjects in the study are limited to records and data, which will be available to the study team. Records include number and duration of counseling calls automatically collected by Optum. Data will be in the form of self-report questionnaires collected on the phone or via the internet and stored in a secure computer assisted telephone interview (CATI) system or via a secure link to a survey collection database. The follow-up survey may be completed via an online secure survey sent by Optum or telephone survey conducted by an external survey team. There will also be biochemical verification of tobacco use at 3 months post randomization. Documentation of verification will be provided to the study team by the participant in the form of a de-identified picture of the test result.

5. Data Analysis

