For the proposed pilot study we plan to use summary statistics (means and proportions) with confidence intervals (CIs), and standard errors (SE), and graphical displays (histograms, pie charts, Box plots, etc.), as appropriate, to describe participant self-reported demographic characteristics, use of tobacco and cannabis, and other tobacco and cannabis variables measured at baseline and/or at each coaching call and at 3-months. We will use Fisher's exact tests, t-tests, and Wilcoxon rank sum tests to compare intervention and control groups. Comparisons including mean number of calls completed, mean satisfaction ratings, mean change in cigarettes per day (CPD), and mean change in days of cannabis use will be completed. We also will compare groups on changes over time on other cannabis measures, including hazardous cannabis use. We will address the effect of missing values on estimated smoking cessation rates using sensitivity analyses for outcome measures: 1) we will analyze responders only, and 2) we will impute missing tobacco use as 'smoking'.

We will have sufficient power with 100 participants (50 per group) and a 70% response to the follow-up interview to detect significant effects of the integrated intervention (vs. standard treatment controls) on feasibility and acceptability of the QL-CBCU intervention as measured by calls completed and treatment satisfaction at 3 months. This sample size is also sufficient for estimating QL-CBCU's potential impact (compared with the standard quitline) measured at 3 months on tobacco abstinence and CB outcomes (motivation to reduce days using CB, confidence in avoiding CB over-use, decreased problems associated with CB use, and decreased frequency of use). The sample sizes for this feasibility study are sufficient for the conduct and reporting of stage I pilot studies and were not selected for purposes of detecting statistically significant group differences at the alpha .05 level on outcomes. Our sample size is sufficient for documenting what power is available. For ordinal measurements that can statistically be treated in a similar manner to "continuous" measures (such as the number of QL calls completed and days used CB), we have 80% power to detect an effect size of 0.68. For proportions, we are powered to detect a difference in proportions of 0.22 to 0.34 (depending on the proportions in the two groups).

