8. DATA HANDLING

1. Data Protection, Storage and Transfer Plan

See mitigations of risk above for Optum data handling processes. In addition:

- Any personal information will be stored as electronic data in password-protected secure computer files, secured from unauthorized access. Data will be kept for at least 6 years after the study ends and related reports are published. Data will be completely destroyed once it is no longer needed.
- Any published results will take the form of summary results; they will not report anything that would identify a specific person.
- The research team at Optum will have access to the study data Only the minimal data required to complete the research will be accessed and analyzed.
- Some study data may be shared with research partners and regulatory bodies. This includes:
 - Researchers at University of Washington
 - Maryland Marketing Source (MMS) who may call you to complete your follow up survey;
 - Office of Human Research Affairs (OHRA) at United Health Group, who oversees our research, and;
 - National Institutes of Health, National Institute of Drug Abuse, who funds our research.
- The parties named above may need to look at study records for this research study and related quality assurance, survey completion, or data analysis. In particular:
 - Co-Investigators at the University of Washington (Drs. [name] and [name] will have access to recordings of study calls to assist with treatment fidelity monitoring. These recordings will be sent via Optum-approved secure file transfer processes following recommendations from Optum Compliance, Privacy and Legal (CPL). Recordings will be deleted following fidelity coding procedures.

 [name] will assist with interviewing participants at the end of their treatment. Interview recordings and notes will be stored on a password protected laptop and transferred to Optum via secure file transfer processes as required by CPL and deleted following study completion.

2. Statistical Analysis

See data analysis section above.

3. Future Utilization

Research findings will be:

- 1. Used to inform product development if found to be effective at helping participants quit tobacco and/or decrease cannabis use.
- 2. Disseminated via peer-reviewed publications and presentations at national conferences.

4. Publication Plan

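### Does the pilot need a named main abstinence analysis, and an arm-specific missing-data model, for the roughly 30% of 3-month outcomes it expects to lose?

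*Combined protocol and SAP*

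**What the plan says.** Section 6.5 is the whole analysis plan; section 8.2 (Statistical Analysis) says only "See data analysis section above". On missing tobacco outcomes it states: "We will address the effect of missing values on estimated smoking cessation rates using sensitivity analyses for outcome measures". The two rules follow: "we will analyze responders only, and 2) we will impute missing tobacco use as" smoking. Fisher's exact test is listed for group comparisons in general, with no analysis set attached.

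The same section assumes 50 per group and 70% response. It gives two planning figures, "we have 80% power to detect an effect size of 0.68" and "we are powered to detect a difference in proportions of 0.22 to 0.34", and says that the sample sizes "were not selected for purposes of detecting statistically significant group differences at the alpha .05 level on outcomes".

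On retention, section 6.3 says: "We will increase retention at the 3 month follow up survey by reminding participants during coaching calls". It adds email notices, 11 telephone attempts by an outside survey company, and a possible final email with a brief-survey option. Section 4 says of the two arms: "Both interventions include 4-5 proactive counseling calls". Section 5.8 pays both arms alike for calls and survey, and section 6.1 says that the telephone survey company does not know the allocation.

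**The concern.** Two analyses are called sensitivity analyses, but nothing is named for them to be sensitivity analyses of. With 15 of 50 outcomes per arm expected to be missing, the choice between them could matter. Hypothesis 3 in section 2 is comparative (more tobacco cessation than usual treatment), and section 8.4 says that the findings may support a bid for a fully powered trial. An estimate chosen after the data are seen could be the flattering one.

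There is a second worry. Responders-only sets the odds ratio of abstinence, non-responders against responders, to 1 in both arms. Missing-as-smoking sets it to 0 in both arms. If the true ratio differs by arm, both estimates can be wrong in the same direction, and their agreement would give false comfort. Reminders given during coaching calls also offer a route to unequal response, because the number of calls completed may differ by arm. Unequal response biases the missing-as-smoking estimate if some non-responders are in fact abstinent.

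**Working it through.** **Inputs.** From section 6.5: 50 per arm and 70% response, so 0.70 × 50 = 35 observed and 15 missing per arm. From section 5.2: up to 230 enrolled, or 115 per arm. The documents give no abstinence rates and no response by arm, so every such rate below is an assumption. Tests are two-sided at 5%.

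**1. The plan's own figures.** A two-sample t-test with effect size 0.68 has power 0.801 at 35 per arm and 0.920 at 50, so the stated 80% reproduces at 35. Fisher's test at 35 per arm needs a difference of 0.217 when the control rate is near zero and 0.341 when it is 0.20, which matches 0.22 to 0.34. At 50 per arm it never needs more than about 0.29. The figures therefore rest on 35 per arm.

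That does not make responders-only the main abstinence analysis. The 0.68 is illustrated by calls completed and days of cannabis use. Calls are logged automatically and do not depend on survey response, so the 70% looks like a general deflation.

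**2. Does having two analyses matter?** Assume no true effect, 70% response in both arms and 30% abstinent in everyone.

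- Sampling SD at 50 per arm, missing-as-smoking: observed rate 0.7 × 0.3 = 0.21; √(2 × 0.21 × 0.79 / 50) = 8.1 points.
- Sampling SD, responders-only: √(2 × 0.3 × 0.7 / 35) = 11.0 points.
- Simulation (20,000 trials): the two estimates correlate about 0.94 and have opposite signs in about 6% of trials.
- They differ by 5 points or more in about 24% of trials at 50 per arm and 8% at 115. Five points is 5 / 11.0 = 0.45 of the responders-only SD.
- Fisher rejection at 50 per arm is about 3% for missing-as-smoking and 3.5% for responders-only. At least one rejects in 4.2% to 4.7% of trials across repeated runs.

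So even an analyst who always picked the more favourable result would stay below 5%.

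**3. Both wrong together.** Take 70% response in both arms and responders 30% abstinent in both. Let non-responders be 10% abstinent under QL-CBCU and 20% under usual treatment.

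- True rates: 0.7 × 0.3 + 0.3 × 0.1 = 0.24 and 0.7 × 0.3 + 0.3 × 0.2 = 0.27.
- True difference: -3 points. Both planned analyses show 0.

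Three points is 3 / 8.1 = 0.37 of the smaller SD. If the odds of smoking in non-responders are anywhere from 1 to 5 times those in responders, set separately by arm, the truth lies between -6.6 and +6.6 points. Even that extreme is below one SD.

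**4. Unequal response.** With r the response and q the abstinence rate among non-responders (1 = QL-CBCU, 0 = usual treatment), the bias of missing-as-smoking is (1 - r₁)(0 - q₁) - (1 - r₀)(0 - q₀) = (1 - r₀)q₀ - (1 - r₁)q₁. Take q = 30% in both arms and 70% response overall.

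| Response gap | Bias (points) | Fisher rejection, 50 per arm | Fisher rejection, 115 per arm |
|---|---|---|---|
| 0 | 0 | 2.9% | 3.5% |
| 5 | 0.05 × 0.3 = +1.5 | 3.1% | 4.2% |
| 10 | 0.10 × 0.3 = +3.0 | 4.0% | 6.4% |
| 20 | 0.20 × 0.3 = +6.0 | 7.4% | 16.1% |

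Rejection passes 5% at 50 per arm only with a 20-point gap. In these cases responders-only is unbiased, so the two planned analyses would tend to disagree and expose the problem.

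**The case for a change.** The strongest case for a change is that a pilot estimate carried into a larger trial should be identified before outcomes are seen, and that reporting two does not say which is carried forward. Enrolment may reach 115 per arm, where a 20-point response gap raises Fisher rejection under missing-as-smoking to 16.1%. The remedy is cheap: a few lines of text and a small table with separate non-responder odds for each arm.

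Part of this stands. No main analysis is named, and agreement between the two rules is not proof of robustness, as the -3 point example shows. Three things weigh against a required change.

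- The route to unequal response is thin. The documents offer both arms the same number of calls and the same payments. Contact by email and by an allocation-blind telephone company does not depend on calls completed. A 20-point gap has no support in the text, and neither does 10% against 20% abstinence in non-responders.
- A table of arm-specific odds would need values that the documents cannot supply, and it discriminates poorly. With odds of 1, 2 and 5 in each arm, all nine cells are positive by chance in 26% of null trials at 50 per arm.
- Naming a missing-data rule would not by itself fix a single result. Table 2 lists both 7- and 30-day abstinence, and verification by mailed saliva test adds a further version.

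The point about one fixed rule for both arms is also scale-dependent. As a difference in rates, missing-as-smoking makes the gap between responders and non-responders equal to each arm's own quit rate, so that gap does vary by arm.

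**Conclusion.** The plan leaves out a detail; it does not contain an error that needs correcting. Followed as written, it yields two openly reported estimates that usually tell the same story. Having both does not inflate false positives at 50 per arm (about 4% to 5% for either). The illustrative biases, 1 to 3 points in the milder cases and 6 to 7 at the extremes, are smaller than the sampling SD of 8 to 11 points. Stating at reporting which estimate leads, and giving response by arm, is ordinary practice that analysts can be expected to follow. An arm-specific missing-data model would add little in a pilot that disclaims significance testing as its purpose.

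This rests on assumed abstinence of about 30%, on response near 70% in both arms, and on the trial being read as a pilot. It would weaken if response differed by something like 20 points between arms, above all at 115 per arm, or if one abstinence estimate were presented as confirmatory.

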7. RISKS AND BENEFITS

1. Risks and Risk Mitigation

STUDY RISKS

- The primary risk of participating in this study is the risk of breach of confidentiality. A breach could potentially occur, for example, if an unauthorized individual accesses the study's database records. Data that the participant sends to the study team via email for biochemical verification could potentially be intercepted or viewed by others, as this data may be transmitted by the participant from an insecure phone or computer. Additionally, some participants may experience emotional discomfort that might occur during discussion of smoking, cannabis use, and impacts on their own health. Persons who quit smoking may experience temporary discomfort associated with nicotine withdrawal symptoms such as irritability, mood changes, headaches, trouble sleeping, and cravings to smoke. Similarly, those who use CB daily or nearly daily and choose to reduce their CB use may experience temporary discomfort associated with withdrawal such as irritability, anxiety, and sleep disturbances.
- Risks of NRT. These are standard QL protocol and not specific to the study. These are detailed by the guit coach during coaching calls, and so are not listed in the **consent form.** As part of standard service offerings from their state or district quitline, nicotine replacement therapy (NRT) in the form of the nicotine patch, gum, or lozenge will be offered to participants in this trial. The study will follow standard NRT protocols as provided through the quitlines. For each participant who opts to use NRT, Optum coaches will assess their medical safety to use NRT and then determine the appropriate dose according to clinical practice guidelines. Optum will then mail the NRT to the participant along with instructions on how to use the medications. The NRT in this trial is being used for its FDA-approved purpose and will be offered to all participants, and therefore, the effect of NRT is not being evaluated as part of the trial, although use of NRT will be assessed at follow-up. As part of standard guitline services, coaches ask about possible side-effects of its use during telephone counseling sessions. According to the FDA-approved product insert, possible side effects associated with the patch include headache, dizziness, lightheadedness, drowsiness, stomach upset, nausea, or flushing the first few days as a user adjusts to the medication. The area around the patch may become red, itchy, or irritated. Rarely, users may experience breathing difficulties, chest pain, irregular heartbeat, nervousness, anxiety, or tremors. Very rarely, a user of the patch may experience an allergic reaction such as a rash, itching, swelling, dizziness, or trouble breathing. Side effects will be disclosed in the study consent form. Optum distributes NRT to 65,000 of its 250,000 callers per year and has established protocols for addressing side effects with callers.

Alternatives to these risks include not participating in the study.

Protections against Risk

• **Protection against breach of confidentiality: security at Optum.**_Optum's quitline business is a HIPAA-covered entity and complies with all HIPAA regulations regarding data security. The Optum offices provide physical and electronic access security, automated backup power for the servers, isolated environmental controls, and fault-warning systems to maintain a stable production environment for their quitline services. Servers, storage appliances, and network components are housed in a dedicated server

room at the corporate headquarters. All electronic and paper records that contain identifiable health information are secured and their use is limited to persons with a direct business-related need for access to this information. All hardware is handled as if it contains protected health information (PHI). Hardware that is no longer used is electronically and physically destroyed. The same security standards that apply to Optum normal business practices will be used to secure data collected for this study. Paper measures will be stored in locked file cabinets. All Service Delivery and Research Staff Members receive biannual Human Subjects training, yearly HIPAA training, sign a confidentiality statement, and are required to adhere to confidentiality and security policies and procedures.

- Distress due to participation in the study intervention or assessment. It is possible that some participants may be upset or embarrassed by participating in the study intervention. Consent scripts will advise potential participants about the study intervention and their right to terminate participation at any time without risk or penalty. Participants are free to refuse to participate in any element of the study or treatment and to refuse to answer any question during the assessments. Expert clinicians are available to counsel any participant who becomes distressed, including Drs. [name] and [name], who are licensed clinical psychologists, and the clinical supervisory team at Optum.
- Nicotine and CB withdrawal. Nicotine and CB withdrawal symptoms are temporary and balanced by long term improvements in health. NRT can help mitigate nicotine withdrawal. Coaches are trained to help participants cope with short-term effects of quitting/reducing tobacco and/or adjust their dose of NRT. Study coaches will be educated about withdrawal symptoms associated with CB reduction or cessation. Although most of these symptoms are similar to nicotine withdrawal, coaches will receive additional training on best ways to help CB users cope with symptoms.
- **NRT side effects.** Participants enrolled in state guitlines have access to nicotine replacement therapy (NRT). Before recommending any medication or dosage, a participant's health condition is assessed with a series of screening questions. Coaches assess medical safety for NRT use by screening for Use Exclusion (UE) factors. Use Exclusions include: diagnoses of heart attack, stroke, or TIA within the past two weeks; being told by a health care provider within the past 6 months of a rapid or irregular heartbeat that required a change in activities or medication; being told by a health care provider in the past 6 months that they have serious or worsening angina; or a previous reaction to patch medication or adhesive tape that caused a rash or hives over the body, swelling of face or throat, wheezing or shortness of breath, or high fever, or that required the participant to discontinue use, or caused irritation that continued after rotating the patch and/or using hydrocortisone cream. If a participant is not eligible for NRT due to a UE, then a Medical Doctor (MD) Override Letter is sent to the participant. Once Optum receives the completed MD Override form from the participants MD and confirms NRT dosing with the participant, Optum sends the participant's NRT shipment. The screening questions were designed by Optum's medical team, and they are intended for use by non-clinical staff to exclude any individuals with specific conditions. Quit Coaches will also educate participants on the utilization of the products and related side effects. Manufacturers' information about side effects is given to the participant in written form and via a 1-800 number that has recorded information. Quit coaches help participants

problem solve around minor side effects (such as minor rash at site of the patch) and recommend that participants seek medical help for more serious side effects.

• There is a six-month delay for participants to re-enroll in quitline services after study involvement to ensure all study data is collected.

2. Benefits

Please describe the benefits of conducting the project.

 All participants may receive some satisfaction or indirect benefit from contributing to this trial. Participation in this research could increase health and quality of life if participants quit smoking and reduce or quit cannabis use. Participants will gain knowledge about quitting and reducing harmful substance use regardless of their quit status. Others may benefit by reduced exposure to second-hand smoke from tobacco or CB products if the participant reduces or quits either substance. If successful, this study could lead to improved tobacco cessation outcomes for those who also use cannabis, which would lead to improved health and longer lives.

